### **9.3.3. *Reporting of Suspected Unexpected Serious Adverse Reactions***

Those SAE which are assessed by sponsor to be SUSAR are to be reported to the EudraVigilance database. The completed CIOMS form will be the basis for the reporting, by the Swedish Medical Products Agency in the EudraVigilance database according to the specified time frames.

Any SAE/pIMD must be reported to the sponsor as soon as possible and not later than 24 h after the site has become aware of the SAE. SUSAR that are fatal or life-threatening are reported as soon as possible and no later than 7 days after the SAE/pIMD has become known to the sponsor. Relevant follow-up information is sent thereafter within an additional 8 days. Other SUSAR are reported as soon as possible and no later than 15 days after they have come to the sponsor's knowledge.

## **9.4. Follow-up of Adverse Events**

Study participants who have been reported with AE/SAE/SUSAR or AESI will be followed up until the condition has resolved or remains stable/persistent and even if the study period has ended.

## **9.5. Independent Data Monitoring Committee**

Not applicable.

## **9.6. Annual Safety Report (ASR)**

Since the sponsor is non-commercial and the marketing authorization holder of the investigational medicinal product is within the EU/EEA the SPC is used as RSI. The simplified template of Annual Safety Report will be used for the ASR reporting.

## **9.7. Procedures in case of emergencies**

Medication errors and use of other medicinal products than those specified in the protocol, including misuse and abuse of the investigational medicinal product, shall be subject to the same reporting obligations as adverse events, as described more detailed in section 9.3. Any failure to produce the expected benefits would also lead to reporting. This would include RSV infection or RSV-related disease. Since no active follow-up for infections is carried out, this aspect is only relevant if any study participant reports such an incident.

If an unforeseen event is likely to have a serious impact on the benefit/risk relationship of the trial, the sponsor and investigator should take appropriate Urgent Safety Measures (USM) necessary to protect the participants. Examples of such measures are to temporarily halt the clinical trial or to introduce supplementary monitoring measures. The sponsor should, via CTIS, inform the concerned Member States about the event and the measures taken. Notification must be made as soon as possible, but no later than seven days after the measures have been taken.

## **10. Statistics**

### **10.1. Analysis population**

The trial intends to include all participants into the analysis for the primary endpoint. A primary per-protocol analysis will be performed and can be complemented by a secondary analysis including all enrolled participants that have received at least one dose of Arexvy.

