LÖF	Landstingens Ömsesidiga Försäkringsbolag
LRTD	Lower Respiratory Tract Disease
mAb/Ab	Monoclonal antibody/Antibody
MGI	Mean geometric increase

Member State	European Union (EU) Member state where an application for authorisation of a clinical trial or of a substantial modification has been submitted.
MPL	3-O-desacyl-4'-monophosphoryl lipid A
mRNA/RNA	Messenger ribonucleic acid/ribonucleic acid
N/A	Not applicable
PBMC	Peripheral blood mononuclear cell
PI	Principal Investigator
pIMD	Potential immune-mediated disease = autoimmune diseases and other inflammatory and/or neurologic disorders which may or may not have an autoimmune etiology
postF	Postfusion
PP	Per Protocol analysis = including only data from participants who have completed the trial in accordance with the protocol, with no deviations from the protocol
preF	Prefusion
RSI	Reference safety information = A list of all known serious adverse reactions for the investigational medicinal product, including severity and frequency of the adverse reaction. The RSI is contained in the Summary of Product Characteristics or IB and is used to determine which adverse reactions should be reported as suspected unexpected serious adverse reactions (SUSARs).
RSV	Respiratory syncytial virus
RSVPreF3	Vaccine antigen; recombinant RSV glycoprotein F stabilized in pre-fusion conformation
SAP	Statistical Analysis Plan
SOP	Standard Operating Procedure
SPC or SmPC	Summary of Product Characteristics
SUSAR	Suspected Unexpected Serious Adverse Reaction = This is an event that is likely related to the investigational medicinal product but with unexpected occurrence. An adverse reaction is

	unexpected if its nature or seriousness is not consistent with the information on the product in the RSI.
Tfh	T follicular helper cell
TMB	3,3 ,5,5 -Tetramethylbenzidine
TNF	Tumor necrosis factor
US	United States
USM	Urgent Safety Measures
VE	Vaccine efficacy

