- Any history of dementia or any medical condition that moderately or severely impairs cognition and understanding of the informed consent form and/or study procedures
- History of chronic alcohol consumption and/or drug abuse as deemed by the investigator to render the potential participant unable/unlikely to provide accurate safety reports or comply with study procedures.

Planned move during the study period that will prohibit participating in the study until study end.

Participation of any study personnel or their immediate dependents, family or household members as well as any family relations to Sponsor or PI.

Co-administration of other vaccines less than 14 days before or after study vaccination. A period of less than 30 days before or after study vaccination applies in the case of Shingrix.

Intervention:	Study participants will be vaccinated at study start and revaccinated 12 months after. The study period is approximately 18 months per study participant, during which 10 blood draws are planned.
Investigational medicinal product(s),	Adjuvanted RSVPreF3 vaccine (trade name Arexvy, manufactured by GSK). Arexvy is a sterile injectable suspension for intramuscular use (0.5 mL) containing

dosage, administration:	120 µg of recombinant RSVPreF3 adjuvanted with AS01E.
Ethical considerations, benefit/risk:	All study participants (60-65 years old and ≥80 years old) will be given Arexvy, an approved vaccine specifically indicated for preventing severe respiratory tract disease in this population. Arexvy has demonstrated a high protective efficacy, and an acceptable reactogenicity and safety profile. The overall benefit/risk balance is positive.
Planned duration of the trial:	Q3 2025 – Q2 2027

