#### **4.6. Exploratory endpoint(s)**

## 5. Trial design and procedure

### 5.1. Overall trial design

[figure not shown]
This is a phase IIIb open-label post-marketing clinical trial using an already approved vaccine in the targeted population group. The design will generate immu[REDACTED]

and maintenance of RSV vaccine-induced immunity in the oldest vaccine recipients. The study includes a prime vaccination and revaccination after one year. [REDACTED]

[REDACTED] The study period is approximately 18 months per study participant. After screening and Informed Consent procedure, 10 visits are planned where one prime dose of vaccine Arexvy (GSK) 0.5 mL i.m is given at the first visit (V1) and a revaccination at the 12-month timepoint (V7). The design and scheduled activities are shown in Figure

1 and Table 1.

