#### ***8.1.1. Methods for the primary endpoint***

The primary endpoint of this trial is defined as the descriptive analysis of the differences in RSV A and B neutralizing antibodies at D31 after prime vaccination in the two age groups enrolled in this study. The primary endpoint will be measured in serum by an established neutralization assay. The assays will be performed at accredited laboratories of GSK. The analysis will be performed after the collection of all D31 samples. A short description of the method can be found in section 16.

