## **10.2. Statistical analyses**

### **10.2.1. Statistical methods**

Descriptive statistics for the primary endpoint will include reporting the geometric mean neutralizing titers (GMTs) against RSV A and B one month (D31) after the prime dose with Arexvy with their corresponding standard deviations for both study groups. In addition, the sero-response rate, defined as the percentage of participants with at least a 4-fold increase from baseline to D31, and the mean geometric increase (MGI) between D31 and D0 after prime will be calculated (equal to the geometric mean of the individual ratio).

The same analysis will be applied to the neutralizing titers for RSV A and B following revaccination, which includes calculation of the sero-response rate following revaccination after one year as well as MGI between D31 after revaccination compared to m12 and the MGI between D31 after revaccination over D31 after prime. Statistical analysis will also include the width of the confidence interval around the GMT.

Safety measurements, such as occurrence of solicited AEs, unsolicited AEs, SAEs or any pIMDs will be reported as frequency counts and percentages in both age groups. Analysis of the intensity, relationship and duration will be performed. Any analysis of other parameters and experimental outcomes will be outlined in a separate statistical analysis plan (SAP).

The results of this study will be interpreted in the context of its exploratory nature and aligned with the descriptive study objectives.

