### **10.5. *Interim analysis (if relevant)***

Given the exploratory nature of the study objectives and that this study employs a licensed vaccine under already approved conditions, no formal interim analysis will be performed. Analysis of the different endpoints and study outcomes will be conducted as the samples are collected and following the priority list given in Table 2 (see section 5.2.).

The primary endpoint will be analysed once all study participants have completed their D31 follow-up visit after prime vaccination. Secondary endpoints regarding safety after prime vaccination can be completed once the 6-month follow-up data has been collected.

For the revaccination timepoints a similar approach will be applied, including a final analysis after reaching the end of the trial.

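### The D31 primary analysis is per-protocol, but the protocol's only per-protocol definition requires trial completion without deviations, which nobody can meet when that analysis is run

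*Protocol*

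**What the plan says.** - **Population.** Section 10.1 opens with "The trial intends to include all participants into the analysis for the primary endpoint" and continues "A primary per-protocol analysis will be performed and can be complemented by a secondary analysis including all enrolled participants", meaning those who received at least one dose.
- **Definition.** Section 10.1 gives no criteria for the per-protocol set. The abbreviation list explains PP as "including only data from participants who have completed the trial in accordance with the protocol, with no deviations from the protocol". No other definition appears in the protocol.
- **Timing.** Section 10.5: "The primary endpoint will be analysed once all study participants have completed their D31 follow-up visit after prime vaccination". Section 8.1.1 agrees: "The analysis will be performed after the collection of all D31 samples".
- **Follow-up.** Section 5.1: "The study period is approximately 18 months per study participant". Table 1 puts revaccination (V7) at month 12 and the last visit (V11) six months later, each with a window of 14 days either way. Section 5.4.3 ends the trial at that last safety visit.
- **Calendar.** The Synopsis gives the planned duration as "Q3 2025 – Q2 2027".
- **Discontinuation.** Section 6.3 permits, with consent, the analysis of data from participants who leave early.
- **SAP.** Section 10.2.1 sends the analysis of other parameters and outcomes to a separate SAP. It does not mention analysis populations.

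**The concern.** The set named as primary is defined by an event, trial completion, that lies well beyond the point at which the primary analysis is to be run. Taken together, the statements on population, definition and timing cannot all be followed.

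There are two ways to read them, and neither works as written. If membership is judged at the D31 analysis, nobody qualifies. If it is judged at trial end, the D31 analysis has to wait for it, and a participant with valid D0 and D31 titres could be removed for leaving, or for a deviation, up to about 17 months after the endpoint was measured. The second reading also sits badly with the aim of including all participants (section 10.1) and with section 6.3.

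At stake is who contributes to the D31 GMTs, the MGI and the sero-response rates. In a descriptive trial these estimates are the main product.

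**Working it through.** **1. The plan's own figure.** Section 10.4 enrols 35-40 in the 80+ group, allowing for 10-20% drop-out and aiming at about 30 per group. With n = 30/(1 - d), rounded up: 30/0.9 gives 34 and 30/0.8 gives 38. The stated range is consistent with this.

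**2. Can anyone have completed the trial by the last D31 visit?** Take the widest reading of the planned duration, 1 July 2025 to 30 June 2027, with 12 months = 365 days, 6 months = 183 days and 30.4 days per month.

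| Step | Nominal visits | Windows set to make the gap smallest |
|---|---|---|
| D0 to completion | 365 + 183 = 548 days | (365 - 14) + (183 - 14) = 520 days |
| First possible completion (1 July 2025 + above) | 31 Dec 2026 | 3 Dec 2026 |
| Last possible D0 (30 June 2027 - above) | 29 Dec 2025 | 26 Jan 2026 |
| Last D31 (last D0 + 31, or + 34 with the 3-day window) | 29 Jan 2026 | 1 Mar 2026 |
| Gap from last D31 to first completion | 336 days, 11.1 months | 277 days, 9.1 months |

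Number meeting the definition when the D31 analysis is due: 0 of 65-70.

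**3. How far would the calendar have to slip?** For even one participant to have completed by the last D31, enrolment would have to last 520 - 34 = 486 days (16.0 months), or 548 - 31 = 517 days (17.0 months) with nominal visits. The planned duration leaves 209 days (6.9 months) and 181 days (6.0 months) respectively.

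**4. What would the trial-end reading cost?** Apply the 10-20% drop-out of section 10.2.2 to the 80+ group and assume that all of it falls after D31, which is the worst case.

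- Of 35: 3.5 to 7 lost, 31.5 to 28 left.
- Of 40: 4 to 8 lost, 36 to 32 left.

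With an unchanged SD of the log titre, the half-width of the 95% CI for the log GMT is proportional to h(k) = t(0.975, k - 1)/sqrt(k).

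- Against everyone enrolled: h(31.5)/h(35) = 1.06, h(28)/h(35) = 1.13, h(36)/h(40) = 1.06, h(32)/h(40) = 1.13.
- Against the planned 30: h(28)/h(30) = 1.04, h(31.5)/h(30) = 0.97, h(32)/h(30) = 0.97, h(36)/h(30) = 0.91.

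The protocol gives no drop-out figure for ages 60-65 and no deviation rate for either group, so losses through the no-deviations clause cannot be calculated.

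**The case against.** The strongest reply is that this is a glossary entry, which section 10.1 neither cites nor repeats, and that detailed criteria for a per-protocol set commonly belong in the SAP. The body of the protocol (analysis after D31, the aim of including all participants, and section 6.3) points towards compliance up to D31 as the intention. Nothing suggests that the sponsor would analyse an empty set.

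Much of this stands. It limits the consequences but does not remove the contradiction: the entry is the only definition given, section 10.1 uses the term without qualification, and a workable D31 set in an SAP would have to depart from it.

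Four stronger readings are tempting and are not supported:

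- **That the primary result will be unobtainable in practice.** The zero follows from the literal wording and is not a forecast. The D31 estimates could also be produced in the all-vaccinated set, though section 10.1 leaves that analysis optional.
- **That the SAP may not define the set.** Section 10.2.1 does not hand the primary-endpoint population to the SAP, but it does not bar the SAP from defining it.
- **That every out-of-window visit after D31 would cost a participant.** Six of the eight visits with a plus-or-minus window (V5, V6, V7, V9, V10, V11) come after D31, and the literal clause covers any deviation. But section 11.4 treats minor deviations separately and links neither kind to the per-protocol set.
- **That the sample becomes too small or the result biased.** Over-enrolment of the 80+ group absorbs the expected drop-out, and the protocol gives no relation between drop-out and titre.

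**Conclusion.** The point holds as a wrongly fixed definition. The protocol's only per-protocol wording cannot be met at the time set for the primary analysis, by a margin of about 9 to 11 months. Deferring membership to trial end breaks the stated timing and allows selection on events after the endpoint was measured.

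Its practical size is modest. The study is descriptive with no power calculation, so no power or error rate is affected. The direction and size of any bias are unknown. Under the trial-end reading, drop-out alone leaves 28 to 36 in the 80+ group, with a log-scale CI width 0.91 to 1.04 times that for 30 participants.

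The timing result assumes that enrolment and follow-up both fit inside the planned duration in the Synopsis. The drop-out result assumes the protocol's 10-20%, all of it after D31, and an unchanged SD. The mismatch in the text is certain; how the sponsor would resolve it in practice is not. It should be corrected, as a matter of wording and not of design.

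**What to change.** 1. In section 10.1, define the D31 per-protocol set by criteria up to D31 only: dose 1 received, valid D0 and D31 neutralisation results, and no deviation up to D31 that is likely to affect the titre.
2. Correct the PP entry in the abbreviation list so that it requires neither trial completion nor the absence of any deviation.
3. Reconcile the stated aim of including all participants (section 10.1) and the permission in section 6.3 with this set, for example by making the all-vaccinated analysis planned instead of optional.
4. Make these changes before D31 data are analysed. The set for the revaccination time points can be defined in the SAP.

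The cost is a few sentences in section 10.1, one abbreviation entry and a consistency check against section 6.3. No extra participants, samples or visits are needed.

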## **10.2. Statistical analyses**

### **10.2.1. Statistical methods**

Descriptive statistics for the primary endpoint will include reporting the geometric mean neutralizing titers (GMTs) against RSV A and B one month (D31) after the prime dose with Arexvy with their corresponding standard deviations for both study groups. In addition, the sero-response rate, defined as the percentage of participants with at least a 4-fold increase from baseline to D31, and the mean geometric increase (MGI) between D31 and D0 after prime will be calculated (equal to the geometric mean of the individual ratio).

The same analysis will be applied to the neutralizing titers for RSV A and B following revaccination, which includes calculation of the sero-response rate following revaccination after one year as well as MGI between D31 after revaccination compared to m12 and the MGI between D31 after revaccination over D31 after prime. Statistical analysis will also include the width of the confidence interval around the GMT.

Safety measurements, such as occurrence of solicited AEs, unsolicited AEs, SAEs or any pIMDs will be reported as frequency counts and percentages in both age groups. Analysis of the intensity, relationship and duration will be performed. Any analysis of other parameters and experimental outcomes will be outlined in a separate statistical analysis plan (SAP).

The results of this study will be interpreted in the context of its exploratory nature and aligned with the descriptive study objectives.

### **10.2.2. *Drop-outs***

A 10-20% of dropouts in the older adult cohort (80+ years) is expected during the study based on previous experience. Enrollment of participants will therefore intend to account for this, including 65-70 participants in total, with 30 participants in the 60-65 years age group and 35-40 participants in the 80+ older adult cohort. The extent of missing data will be reported.

### **10.3. *Adjustments of significance and confidence interval***

Not applicable

### **10.4. *Sample size calculations***

This study is primarily designed to gather descriptive immunogenicity data in older adults upon vaccination with Arexvy, including adults of 80 years of age and older for which data is currently limited. As the study objective is purely descriptive rather than to demonstrate efficacy or test a hypothesis, no formal power-based sample size calculation has been made.

A sample size of 30 individuals in the 60-65 years group and of 35-40 individuals in the 80+ years group was chosen based on feasibility of recruitment, clinical judgement and a 10-20% drop-out expected in the older age group. This sample size of approximately 30 individuals per age group is expected to generate valuable immunogenicity data in an otherwise understudied population and to allow for exploratory comparisons between age groups. Given the descriptive nature of the study, its findings will be interpreted as preliminary.

### **10.5. *Interim analysis (if relevant)***

Given the exploratory nature of the study objectives and that this study employs a licensed vaccine under already approved conditions, no formal interim analysis will be performed. Analysis of the different endpoints and study outcomes will be conducted as the samples are collected and following the priority list given in Table 2 (see section 5.2.).

The primary endpoint will be analysed once all study participants have completed their D31 follow-up visit after prime vaccination. Secondary endpoints regarding safety after prime vaccination can be completed once the 6-month follow-up data has been collected.

For the revaccination timepoints a similar approach will be applied, including a final analysis after reaching the end of the trial.

## **11. Quality Control and Quality Assurance**

### **11.1. Quality Assurance and Sponsor oversight**

The sponsor's quality-related work is based on a risk analysis of the trial as a whole: design, conduct, data collection, evaluation, reporting and archiving. The sponsor will perform quality assurance and quality control activities for the trial; however, responsibility for the accuracy, completeness, and reliability of the trial data presented to the sponsor lies with the PI (and delegate(s)) generating the data.

### **11.2. Monitoring**

The trial will be monitored by an independent monitor before the trial begins, during the conduct of the trial, and after the trial has been completed. This is to ensure that the trial is carried out according to the protocol, that data are reliable and collected, documented, and reported according to ICH-GCP and applicable

ethical and regulatory requirements. Monitoring will be risk-based, which means that the extent of the monitoring is based on the sponsor's risk-assessment and is performed as per the trial's monitoring plan. The monitoring is intended to ensure that the participant's rights, safety, and well-being are met and that data in the CRF are complete, correct, and consistent with the source data.

### **11.3. Source data**

The investigator must keep source documents for each participant in the trial. A document describing what has been classified as source data in the trial (source data reference document) should be included in the Investigator Site File (ISF). The investigator must ensure that all source documents are accessible for monitoring and other quality control activities.

Source data is defined before trial start at each individual site and can, in cases where source data is not registered in another document, consist of the CRF. This should be decided in consultation with the monitor and clearly stated in the source data reference document.

Access to trial-related documentation, such as participants' medical records, CRFs, other source data and other trial documentation will be provided for monitoring and auditing purposes. Access to participants' medical records will require a confidentiality agreement to be signed by the person in charge of the medical records at the trial site and by the monitor and auditor, if applicable. Access will also be granted in the context of regulatory inspections.

